#### 2.1 Sample size calculation

The primary outcome measure for the power calculation is the change of BMI between baseline and after the intervention. The sample size estimation is within the framework of Wilcoxon signed-rank test. Power analysis was conducted in G\*Power to determine a sufficient sample size using an alpha of 0.05, a power of 0.80, a medium effect size (dz = 0.5), and two tails [4]. Based on the aforementioned assumptions, the desired sample size is 35. We have conservatively assumed that the overall dropout rate will be 30% during the 4-week study period. To account for loss to follow-up, the power will be 80% if 50 study subjects are recruited.

# 3. Aims and objectives

The purpose of this intervention study is to evaluate the effect of calorie restriction on BMI loss, amino acid, and gut microbiota in healthy volunteers of two different enterotypes and provide useful insights for potential application of gut microbiome stratification in personalized nutrition intervention.

# 4. Outcomes

This section will present the outcomes investigated to answer the study aims and objectives. The analyses are described in section 3 Analyses.

#### 4.1 Primary outcome

BMI. It will be measured at baseline, CR intervention period.

#### 4.2 Secondary outcomes

#### **Blood amino acids**

Blood samples of each volunteer will be collected at the investigators' study center at baseline and after the 3-week CR intervention. The concentrations of 31 blood amino acids and derivatives in the fasting serum samples will be measured by LC-MS/MS.

#### Amino acids

- 1-Methyl\_histidine
- 2-aminoadipic acid
- 3-Methyl\_histidine

- Alanine
- Arginine
- Argininosuccinic
- Asparagine
- Aspartate
- Citrulline
- Cysteine
- Ethanolamine
- Glutamate
- Glutamine
- Glycine
- Histidine
- Hydroxyproline
- Isoleucine
- Leucine
- Lysine
- Methionine
- Ornithine
- Phenylalanine
- Proline
- Serine
- Taurine
- Threonine
- Tryptophan
- Tyrosine
- Valine
- α-aminoisobutyric acid
- β-Alanine

# Gut microbiota

Fecal samples of each volunteer will be collected at the investigators' study center at

baseline and after the 3-week CR intervention. The gut microbial composition will be determined using shotgun metagenomics sequencing of fecal DNA.

# 5. Populations to be analyzed

41 participates will be analyzed in this study.

#### 6. Analyses

All outcomes will be presented using descriptive statistics: Wilcoxon rank-sum test is used to detect the significant differences on phenotypes, the concentrations of blood amino acids and the relative abundances of genera and species between enterotypes. Wilcoxon signedrank test is used to detect the significant differences on phenotypes, the concentrations of blood amino acids and the relative abundances of genera and species in paired samples before and after the intervention. Permutational multivariate analysis of variance (PERMANOVA) is used to detect the association between enterotypes and the overall blood amino acid profile at baseline by using PERMANOVA with 9,999 permutations on enterotypes. Principal coordinate analysis is used to visual overall gut microbial based on the relative abundance profiles between baseline and after the intervention. Principal component analysis is used to visual overall amino acid composition based on the blood amino acid profiles between baseline and after the intervention. To investigate whether we could predict BMI loss ratio using omics features, we will perform a Lasso (Least absolute shrinkage and selection operator) regression analysis between baseline relative abundances of gut common species and the concentrations of blood amino acids (independent variables), and BMI loss ratio (dependent variables). We first normalize values of both independent and dependent variables (R, scale function). We then use the R function cv.glmnet to choose the most appropriate value for  $\lambda$  in the Lasso model (R glmnet package, alpha =1, family="gaussian", nfolds=10, alpha=1, nlambda=100). Here,  $\lambda$  is the tuning parameter ( $\lambda > 0$ ) which controls the strength of the shrinkage of the variables. We then apply the Lasso feature selection process by shrinking the Lasso regression coefficients of non-informative variables to zero and selecting the variables of non-zero coefficients. To reduce overfitting with a limited sample size (n=41), we apply leave-one-out cross

validation (LOOCV) to estimate the prediction performance of BMI loss ratio using a generalized linear model (GLM) of the selected features (creatFolds function in R caret package and the glm function in R base package). Likewise, we also use baseline BMI values for LOOCV to estimate its prediction performance for CR-associated BMI loss ratio. Spearman's rho values will be calculated between actual BMI loss ratios and the predicted values. P-value adjustment is applied for multiple hypothesis testing on the concentrations of blood amino acids, the relative abundances of gut microbial genera and species use Benjamini-Hochberg (BH) method. R 3.5.0 will be used for all statistical analysis.

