2.1 Background

Calorie restriction (CR), which has the potential effect on weight loss and blood amino acids, has been demonstrated to associate with gut microbiota in human, especially in obese individuals [1, 2]. Observational studies with long-term CR found that CR resulted in weight loss and decreasing chronic disease risk factors in nonobese persons [3-6]. A 4week CR intervention improved gut barrier integrity, reduced systemic inflammation on gut microbial diversity and BMI loss in obese women, suggesting a potential association among gut microbiota, CR and BMI [7]. Enterotype, a concept for stratifying individuals based on the gut microbiota, was first described in 2011 and was closely linked to longterm dietary patterns [8, 9]. Plenty of studies have reported that individuals have shown microbial-dependent (enterotypes, *Bacteroides* to *Prevotella* ratio) metabolic responses to the same intervention, including changes of BMI and glycemic indices [9-14]. As for the association between CR and blood amino acids, Biolo et.al reported changes in blood amino acids of 9 healthy nonobese men after a 2-week CR diet [15]. Despite the plenty of studies on CR as we mentioned above, to our knowledge, there are no studies for simultaneously evaluating impacts of CR on BMI, gut microbiota and blood amino acids in nonobese individuals in a single study.

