4.1 Primary and secondary outcomes

The primary outcomes for this study are:

- Change in BMI of all volunteers (n=41) following calorie restriction dietary intervention
- Different changes in BMI between enterotypes *Bacteroides* (n=28) and enterotypes *Prevotella* (n=13) following calorie restriction dietary intervention

BMI was measured via the clinic scale. To avoid intra-individual variations, BMI was collected multiple times of each volunteer during the last week of the CR intervention, and the averaged BMI value was used as his/her after-intervention BMI.

The secondary outcomes for this study are:

- Change in the concentration of 31 blood amino acids of 36 volunteers following calorie restriction dietary intervention
- Different in the concentration of 31 blood amino acids between enterotypes *Bacteroides* (n=25) and enterotypes *Prevotella* (n=11) following calorie restriction dietary intervention
- Change in the gut microbiota of all the volunteers (n=41) following calorie restriction dietary intervention
- Different in the gut microbiota of between enterotypes *Bacteroides* (n=28) and enterotypes *Prevotella* (n=13) following calorie restriction dietary intervention

The concentrations of 31 amino acids and derivatives in the fasting serum samples were measured by LC-MS/MS. Fasting blood samples were collected before and after the

intervention for amino acid analysis. These blood samples were then centrifuged, and serum samples were collected and stored at -80 °C. The concentrations of 31 amino acids and derivatives in the serum samples were then measured via ultra-high pressure liquid chromatography (UHPLC) coupled to an AB Sciex Qtrap 5500 mass spectrometry (AB Sciex, US) as described previously [19].

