The gut microbial composition was determined using shotgun metagenomics sequencing of fecal DNA. Fecal samples were self-collected and then transferred to the laboratory on dry ice and kept frozen at -80°C before and after the CR intervention. Fecal DNA was extracted following a manual protocol as described previously [20]. The DNA concentration was estimated by Qubit (Invitrogen). Library construction and shotgun metagenomic sequencing were performed on qualified DNA samples based on the BGISEQ-500 protocol in the single-end 100bp mode [21]. Raw reads of BGISEQ-500 with SE100 mode were trimmed by an overall accuracy (OA) control strategy to control quality [21]. After trimming, averagely, 98.15% of the raw reads remained as high-quality reads. By using SOAP2.22 software, the high-quality reads were aligned to hg19 to remove reads from host DNA (identity ≥ 0.9). The retained clean reads were aligned to the integrated non-redundant gene catalog (IGC) using SOAP2.22 [22] and the average mapping rate and unique mapping rate were 80.18% and 65.76% respectively (identity ≥ 0.95). The relative abundance profiles of genes, genera, species and Kyoto Encyclopedia of Genes and Genomes orthologous groups (KEGG, KOs) of each sample were calculated by summing the relative abundances of their assigned IGC genes [22].

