# Abbreviations

CR	Calorie restriction
BMI	Body mass index
ETB	Enterotype Bacteroides
ETP	Enterotype Prevotella
BH	Benjamini-Hochberg
LC-MS/MS	Liquid chromatography-mass spectrometry
Lasso	Least absolute shrinkage and selection operator
LOOCV	leave-one-out cross validation
GLM	generalized linear model
PERMANOVA	Permutational multivariate analysis of variance

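### SAP 6 tests Bacteroides and Prevotella taxa between two groups that were very probably formed from those same taxa, and does not set them apart

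*SAP*

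**What the plan says.** SAP 6 uses the Wilcoxon rank-sum test for "the relative abundances of genera and species between enterotypes". Protocol 6.1 has the same text. SAP 6 then adjusts p-values for "the relative abundances of gut microbial genera and species use Benjamini-Hochberg (BH) method". Neither document excludes a taxon or treats Bacteroides or Prevotella separately. Neither says whether baseline levels, post-CR levels or changes are compared.

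The test serves the fourth secondary outcome in Protocol 4.1, "Different in the gut microbiota of between enterotypes" Bacteroides (28) and Prevotella (13), assessed after CR.

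On the origin of the groups:
- Protocol 2.1 introduces "Enterotype, a concept for stratifying individuals based on the gut microbiota" and reports from earlier work that "individuals have shown microbial-dependent (enterotypes, *Bacteroides* to *Prevotella* ratio) metabolic responses to the same intervention".
- The SAP abbreviations name one group "Enterotype Bacteroides" and the other after Prevotella.
- The only microbiota data described are the fecal shotgun profiles at the two visits (SAP 4.2, Gut microbiota). From these come "The relative abundance profiles of genes, genera, species" and the other profiles listed in Protocol 4.1.

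Neither document states the assignment rule or which visit's sample was used.

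**The concern.** If the two groups were formed from Bacteroides and Prevotella abundances, testing those abundances between the groups tests the grouping against itself. A small p-value is then expected whether or not CR did anything.

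The outcome concerns what follows CR, so a post-CR level difference in these taxa could be listed as a result of the intervention. If enterotypes are real clusters, that difference is true but was there before CR began. The same caution applies to any taxon: a post-CR level difference may be pre-existing and is not by itself evidence of a different response. The study aims to inform stratified nutrition, so confusing a standing difference with a response bears on how this outcome is read.

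**Working it through.** **Inputs from the documents.** Groups of 28 and 13, total 41 (Protocol 4.1); rank-sum test with BH (SAP 6). The documents give no figure for this analysis: no assignment rule, number of taxa, FDR level or between-visit repeatability. The one design figure, 35 evaluable and 35/(1 - 0.30) = 50 recruited (SAP 2.1), reproduces, but it belongs to the paired BMI change and has no bearing here.

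**Assumptions.** Normal log abundances; the 13 subjects with the highest log Prevotella minus log Bacteroides at baseline form the Prevotella group; no CR effect; between-visit reliability r = 0.5 to 0.9; 2 defining genera in a BH family of 20, 50 or 100 taxa; FDR 0.05. Two cases: no true clusters, and clusters 3 units apart on the log ratio. 3,000 runs in each of 18 settings.

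**Expected size without clusters (large-sample approximation).**
- Fraction in the smaller group: 13/41 = 0.317. The normal cut-point is 0.476, with density 0.356.
- Gap between group means on the log ratio: 0.356/0.317 + 0.356/0.683 = 1.12 + 0.52 = 1.64 SD.
- The log ratio of two independent genera has √2 times the SD of one genus, so the baseline gap per genus is 1.64/√2 = 1.16 SD, from the split alone.
- Post-CR gap: r × 1.16, or 0.58 SD at r = 0.5 and 1.04 SD at r = 0.9.
- Bias in mean change from regression to the mean: (1 - r) × 1.16, or 0.58 SD at r = 0.5 and 0.12 SD at r = 0.9. The simulation gave 0.11-0.58 SD.

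At the extreme, complete separation of 13 from 28 gives an exact two-sided p of 2/C(41,13) ≈ 1.1 × 10⁻¹⁰.

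**Simulated rejection rates for the defining genera, no CR effect.**

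| Comparison | No clusters | Clusters |
|---|---|---|
| Baseline level, at least one significant after BH | 81-99% | about 100% |
| Post-CR level, at least one significant after BH | 4-88% | 68-100% |
| Change, unadjusted p<0.05 per genus | 10-38% | 7-15% |
| Change, at least one significant after BH | 0-17% | 0-3% |

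If the post-CR sample assigned the groups, the first two rows swap. Including repeat runs, the range for unadjusted change is about 6-38%.

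**Effect on the other taxa.** With the two genera in the family, the chance of any false hit among the rest was 6-14% at baseline and 2-13% post-CR, against 2-5% with them left out. Whole-family FDR stayed at 4.1-5.1%.

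**Which test suits the remaining taxa.** Take a non-defining taxon with a stable enterotype gap D and no CR effect. Expected change is zero in both groups. Adjusting post-CR for baseline removes only about r × D, leaving (1 - r) × D: for D = 1.5 SD, 0.15 SD at r = 0.9 and 0.75 SD at r = 0.5. In simulation, rank ANCOVA gave unadjusted p<0.05 in about 7-56% of runs for gaps of 0.5-1.5 SD. Rank-sum on change gave 4-6%.

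**The case against.** **The premise is inferred.** This stands. Protocol 2.1 speaks of earlier studies and does not define this trial's groups, so circularity is very probable but not documented. A reader might infer that the rule is known to be the ratio of the two genera; the documents do not say so. That is why stating the rule belongs in the fix.

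**The striking percentages are for baseline levels, while the outcome is set after CR.** This also stands. The post-CR range of 4-100% is too wide to size the problem, and change is much less affected.

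**BH is not broken.** Correct. A reader might infer that the defining taxa invalidate the adjustment for all the others. The documents do not support this: BH controls whole-family FDR, which holds, and the SAP promises no family-wise control over a subset. Much larger spillover appears only if tens of defining taxa with near-zero p-values share the family, and nothing in the documents indicates that.

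**Few readers would be misled by more Prevotella in a group named after Prevotella.** Largely true for the genus. However, the SAP describes these tests as detecting significant differences and does not call them a check of the grouping. The same issue reaches individual species, where it is less visible.

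**Barring every test of the two genera would go too far.** Accepted. Whether they change differently under CR is part of the outcome, so change is kept as exploratory.

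**Conclusion.** The point holds in a limited form. As written, SAP 6 can list the grouping itself as a between-enterotype finding, because it sets no taxon apart and does not say whether levels or changes are tested. The size rests on the assumed rule, reliability and number of taxa.

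A reader might go further and doubt the trial's main results. The documents do not support that: the BMI outcomes, the amino acid outcomes and the before-after tests in all 41 do not test the taxa that form the groups against those groups. Severity is minor, confined to one secondary outcome. Label: cheap improvement.

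**What to change.** In SAP 6:

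1. Report baseline and post-CR level comparisons of Bacteroides, Prevotella and their species between enterotypes descriptively, as a check of the grouping, outside the inferential tests and the BH family.
2. For the post-CR outcome in the remaining taxa, rank-sum test the within-person change (post-CR minus baseline, for example on the log scale) between enterotypes. Do not use the post-CR level alone or rank ANCOVA, which can report a stable difference as a response.
3. Report change in the defining taxa as exploratory, with a caveat on regression to the mean if the baseline sample assigned the groups.
4. State the assignment rule and the sample used, so that the set-apart taxa are defined. If the whole genus profile was used, label all between-enterotype genus level comparisons as descriptive.

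Leave the before-after tests in all 41 as planned. The cost is fewer taxa formally tested between enterotypes and a little more analysis work; no new data are needed.

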5.1 Detailed study procedures

5.1.1 Screening information

Screening information			
Step	Descriptor	Details	Appendix
1	Statement of Informed Consent	Each participate must read, understand and sign the Statement of Informed Consent before enrolled in the study. The Principal Investigator or designer conducting the informed consent discussion must sign the consent form. Note: the participate must be provided with a signed copy of this document.	
2	Demographics	Age, sex, height, weight, body mass index	
3	Healthy history	Record the participates' dietary and medical and international travel history	
4	Eligibility at screening	All responses to Inclusion Criteria questions must be answered "yes", and all responses to Exclusion Criteria questions must be answered "no" for the participate to be considered eligible	

5.1.2 Baseline period for recruiting participates.

Baseline information				
Step	Descriptor	Details	Appendix	
1	Baseline clue	Participate will complete the baseline clue measures regarding their own contact dietary habits.	exclude 9 participates	
2	BMI clue	Record participates' BMI.		
3	Measuring BMI	BMI was measured via the clinic scale.		
4	Collecting Fasting blood samples	Fasting blood samples were collected at the end of baseline for extracting amino acids	5 participates without fasting blood	

5	Collecting fecal samples	Fecal samples were self-collected and then transferred to the laboratory on dry ice and kept frozen at -80°C at baseline.	
6	Eligibility after Baseline Examination	All responses to Inclusion Criteria questions must be answered "yes", and all responses to Exclusion Criteria questions must be answered "no" for the participate to be considered eligible.	

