6.1 Statistical methods to be employed

All outcomes will be presented using descriptive statistics: Wilcoxon rank-sum test is used to detect the significant differences on phenotypes, the concentrations of blood amino acids and the relative abundances of genera and species between enterotypes. Wilcoxon signedrank test is used to detect the significant differences on phenotypes, the concentrations of blood amino acids and the relative abundances of genera and species in paired samples before and after the intervention. Permutational multivariate analysis of variance (PERMANOVA) is used to detect the association between enterotypes and the overall blood amino acid profile at baseline by using PERMANOVA with 9,999 permutations on enterotypes. Principal coordinate analysis is used to visual overall gut microbial based on the relative abundance profiles between baseline and after the intervention. Principal component analysis is used to visual overall amino acid composition based on the blood amino acid profiles between baseline and after the intervention. To investigate whether we could predict BMI loss ratio using omics features, we will perform a Lasso (Least absolute shrinkage and selection operator) regression analysis between baseline relative abundances of gut common species and the concentrations of blood amino acids (independent variables), and BMI loss ratio (dependent variables). We first normalize values of both independent and dependent variables (R, scale function). We then use the R function cv.glmnet to choose the most appropriate value for λ in the Lasso model (R glmnet package, alpha =1, family="gaussian", nfolds=10, alpha=1, nlambda=100). Here, λ is the tuning parameter ($\lambda > 0$) which controls the strength of the shrinkage of the variables. We then apply the Lasso feature selection process by shrinking the Lasso regression coefficients of non-informative variables to zero and selecting the variables of non-zero coefficients. To reduce overfitting with a limited sample size (n=41), we apply leave-one-out cross validation (LOOCV) to estimate the prediction performance of BMI loss ratio using a generalized linear model (GLM) of the selected features (creatFolds function in R caret package and the glm function in R base package). Likewise, we also use baseline BMI values for LOOCV to estimate its prediction performance for CR-associated BMI loss ratio. Spearman's rho values will be calculated between actual BMI loss ratios and the predicted values. P-value adjustment is applied for multiple hypothesis testing on the concentrations

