# 7. Missing data

In this study, data of 5 participates' blood amino acids was missing at baseline and after the intervention. For a specific analysis, the study participates with missing data on the blood amino acids will be excluded from the analysis.

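### The enterotype comparisons of blood amino acids contain enterotype only, so a sex or age difference can be credited to enterotype, and power can be lost if sex explains amino-acid variance

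*SAP*

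**What the plan says.** SAP section 6 states that PERMANOVA "is used to detect the association between enterotypes and the overall blood amino acid profile at baseline", and that this is done "by using PERMANOVA with 9,999 permutations on enterotypes". Protocol 6.1 has the same text ("PERMANOVA with 9,999 permutations on enterotypes"). For single analytes the SAP states: "Wilcoxon rank-sum test is used to detect the significant differences on phenotypes, the concentrations of blood amino acids", with enterotype as the grouping. A rank-sum test takes no covariates. Neither document names a covariate, stratum, restricted permutation or adjusted sensitivity analysis for these comparisons. Benjamini-Hochberg (BH) adjustment is planned for the amino acids.

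The comparison is a listed secondary outcome in Protocol 4.1 ("Different in the concentration of 31 blood amino acids between enterotypes"), with 25 *Bacteroides* and 11 *Prevotella* participants. The screening table in Protocol 5.1.1 records "Age, sex, height, weight, body mass index". Sex and age are summarised only for the whole cohort of 41: 24 women, 17 men, age 30 ± 6.

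**The concern.** Nothing in the design balances sex or age over the enterotypes. If men and women differ in some amino acids and the sex mix differs between the 25 and the 11, an enterotype-only test attributes part of the sex difference to enterotype. If the sex mix is similar, sex variation stays in the residual and can hide a real difference. BH handles the number of tests and does nothing about confounding. The study aims to support stratifying people by gut microbiome, so a sex difference reported as an enterotype difference would mislead on that aim. Readers could not detect it, because neither sex nor age is shown by enterotype.

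**Working it through.** **Inputs from the documents.** 31 analytes (SAP 4.2); 41 − 5 = 36 people with amino-acid data (SAP 7); 25 v 11 (Protocol 4.1); 24 women and 17 men (SAP 2).

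**Assumptions, because the documents are silent.** Men among the 36: 36 × 17/41 = 14.9, taken as 15. Analytes standardised to SD 1. Sex effect d of 0.6 or 1.0 SD in half the analytes. Common inter-analyte correlation 0.1 or 0.3. Euclidean distance. Adjustment was simulated for sex only.

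**1. The plan's own figure.** SAP 2.1 asks for 35 evaluable and 50 recruited. A signed-rank test with dz = 0.5, two-sided 0.05 and efficiency 3/π has power 0.801 at n = 35, and 35/(1 − 0.30) = 50. Both figures reproduce, but they cover only the paired BMI change. No figure is given for the enterotype comparisons.

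**2. How likely is an imbalance by chance?** Hypergeometric, 15 men of 36, with 11 in the smaller group:

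| Men, *Bacteroides* v *Prevotella* | Gap in share of men | Chance of this gap or larger, either direction |
|---|---|---|
| 10/25 v 5/11 | 0.455 − 0.400 = 0.055 | the closest to balance possible |
| 8/25 v 7/11 | 0.636 − 0.320 = 0.316 | 14% |
| 7/25 v 8/11 | 0.727 − 0.280 = 0.447 | 2.5% |

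**3. Bias per analyte.** The expected unadjusted difference with no enterotype effect is d × gap. At d = 1.0 this is 0.32 SD and 0.45 SD in the two imbalanced rows. Simulated null rejection of the rank-sum test for one sex-linked analyte, two-sided 0.05, **before BH** (20,000 runs):

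| Men | d = 0.5 | d = 0.8 | d = 1.0 |
|---|---|---|---|
| 8/25 v 7/11 | 5.4% | 7.2% | 8.8% |
| 7/25 v 8/11 | 7.5% | 11.9% | 15.8% |

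A linear model with enterotype and sex stays at 4.7-5.2%. After BH, with no enterotype effect, the chance of any rejection among the 31 is about 4-6% and 6-11% in the two rows.

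**4. PERMANOVA with no enterotype effect** (repeated runs, 300 to 1,000 data sets per setting, d = 0.6 or 1.0). Unadjusted rejection is about 7-14% at 8/25 v 7/11 and about 10-37% at 7/25 v 8/11. Adjusted for sex it is 4-6% in the larger runs and 3-9% in the smallest. Permuting within sex instead, at d = 1.0 and correlation 0.3, lowers rejection from 8.0% to 4.7% and from 18.5% to 4.3%.

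**5. Power when sex is nearly balanced.** For one analyte with an enterotype effect of 1 SD, power = Φ(1/SE − 1.96), where SE = s√(1/25 + 1/11) = 0.362s. Unadjusted, s = √(1 + d² × (21/36)(15/36)); adjusted, s = 1.

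| d | s | Unadjusted | Adjusted |
|---|---|---|---|
| 0 | 1.000 | 0.789 | 0.789 |
| 0.5 | 1.030 | 0.765 | 0.789 |
| 0.8 | 1.075 | 0.729 | 0.789 |
| 1.0 | 1.115 | 0.698 | 0.789 |

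For the PERMANOVA at 10/25 v 5/11, with an enterotype shift of 0.6 SD in the analytes not linked to sex (1,000 data sets per setting):

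| Correlation | d = 0.6 | d = 1.0 |
|---|---|---|
| 0.1 | 87% to 91% | 76% to 90% |
| 0.3 | 51% to 56% | 51% to 60% |

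Another run of the same settings gave gains of 5 to 6 points at d = 0.6 and 15 to 16 points at d = 1.0.

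**6. What adjustment costs.** Imbalance inflates the variance of the adjusted estimate by 1/(1 − r²), with r² = gap² × (25/36)(11/36)/[(21/36)(15/36)]. This is 1.10 at a gap of 0.316 and 1.21 at 0.447. With an enterotype shift of 0.6 SD and **no** sex effect (800 runs), PERMANOVA power at correlations 0.1 and 0.3 changes as follows:

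| Men | Correlation 0.1 | Correlation 0.3 |
|---|---|---|
| 10/25 v 5/11 | 88% to 88% | 54% to 54% |
| 8/25 v 7/11 | 90% to 86% | 55% to 51% |
| 7/25 v 8/11 | 91% to 80% | 54% to 45% |

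**The case against.** The strongest reply is that nothing in the documents shows a link between sex and enterotype. If there is none, averaging over all possible splits gives null rejection of about 4.6% for the rank-sum test and 4.9-5.7% for the PERMANOVA, so there is no overall inflation. That stands. The rates in the working are conditional on the split that the sample happens to have, and the worst split shown is rare by chance. But the split will be known for the actual 36 people, and a real association between sex and enterotype is not excluded.

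A reader might infer that the planned tests lose power in any case. They do not. With no sex effect nothing is gained by adjusting, and when imbalance runs in the same direction as the enterotype effect the unadjusted test rejects more often (0.88 v 0.72 for one analyte at 8/25 v 7/11 men, d = 1.0), partly through bias. Nor does adjustment repair everything free of charge, as step 6 shows.

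A reader might also point to the intake on the restricted diet, 1000 kcal/day for women and 1200 for men. The PERMANOVA is at baseline, before restriction, so this difference cannot affect it. It bears only on post-intervention comparisons, and both intakes are described as about half of normal.

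Finally, replacing the rank-sum tests outright with log-linear models would be partly a matter of preference. That is accepted: the planned tests can stay, with adjusted results beside them.

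**Conclusion.** The point holds as a conditional one about secondary outcomes. The PERMANOVA and the 31 rank-sum tests have enterotype as their only term, enterotype is not randomised, and sex and age are available. Possible misattribution is the stronger ground; lost power is the weaker one.

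Under assumed sex effects of 0.6 to 1.0 SD in half the analytes, PERMANOVA null rejection is about 7-14% at a moderate imbalance and about 10-37% at a severe one, against roughly 5% after adjustment for sex. With sex nearly balanced, adjustment adds about 4 to 15 points of power. Per-analyte rates are lower once BH is applied. The size rests on the assumed sex effect, correlation and sex split, none of which the documents give. The benefit of adjusting for age was not quantified. The documents do not show that confounding has occurred, or that the planned tests are invalid on average.

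**What to change.** In SAP section 6 and Protocol 6.1:

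- Fit the PERMANOVA on sex + age + enterotype, with enterotype tested last and the same 9,999 permutations.
- Tabulate sex and age by enterotype for the 36 people with amino-acid data.
- Keep the 31 rank-sum tests, and beside each report a comparison adjusted for sex and age (a linear model on the log or rank scale) or, for sex alone, a sex-stratified van Elteren test. Apply BH across the 31.
- State that a difference will be called an enterotype difference only if it persists after adjustment.

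The cost is SAP and protocol wording, a few lines of code and two degrees of freedom out of 36 people. Some power is also lost if sex is imbalanced but unrelated to amino acids, up to about 11 points in the simulations. With 11 people in the smaller group, the covariates should stop at these two.

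### The Lasso penalty is tuned on a random 10-fold split that the plan does not fix or repeat, so how many omics features are selected, and sometimes whether any are, depends on that split

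*SAP*

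**What the plan says.** SAP section 6 and Protocol 6.1 describe the prediction analysis in the same terms. The BMI loss ratio is regressed by Lasso on baseline abundances of common gut species and on blood amino acid concentrations. On tuning, the text reads "We then use the R function cv.glmnet to choose the most appropriate value for" λ, and the arguments include "nfolds=10, alpha=1, nlambda=100". Features are then chosen by "selecting the variables of non-zero coefficients".

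Performance comes afterwards: "To reduce overfitting with a limited sample size (n=41), we apply leave-one-out cross" validation, applied to a GLM of the features already selected. Spearman's rho between observed and predicted loss ratios is calculated, and baseline BMI is assessed as a predictor in the same way.

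SAP section 7 reports that five participants' data on "blood amino acids was missing at baseline and after the intervention", and excludes them from analyses that need those data.

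The glmnet arguments are listed in some detail. Repeated cross-validation, a fold assignment, a seed, and a choice between lambda.min and lambda.1se are not mentioned in either document.

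**The concern.** When no fold assignment is supplied, cv.glmnet allocates people to folds at random. With about 36 people in 10 folds, the cross-validated error curve is noisy, and its minimum can move a long way along the λ grid from one allocation to the next. Two analysts who follow the SAP on identical data could therefore report feature lists of different length, or one could report a list and the other none.

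The rho that is set beside that of baseline BMI would inherit the same arbitrariness. The Lasso is the only planned analysis that predicts an individual's BMI loss from omics data, so it bears on the stated aim of informing personalized nutrition.

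**Working it through.** **The plan's own figures.** None is given for the Lasso. The only design figure is the BMI sample size in SAP 2.1, and it reproduces: 35 analysed, and 35 / (1 − 0.30) = 50 recruited. It is not affected by this point.

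**Inputs from the documents.**
- Complete cases for the joint species and amino acid model: 41 − 5 = 36, which agrees with the 36 volunteers in Protocol 4.1. The n=41 in SAP section 6 would fit a species-only model.
- Fold sizes with 10 folds: at n=36, six folds of 4 and four of 3 (24 + 12 = 36). At n=41, one fold of 5 and nine of 4 (5 + 36 = 41).
- Amino acids: 31. The number of common species is not stated.

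**Assumptions.** 50, 100 or 200 species, so p = 81, 131 or 231 with the 31 amino acids. Gaussian features in blocks of 10 with correlation 0.3. Either no signal, or three true predictors with R² of 0.3 or 0.6.

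**Simulation.** cv.glmnet with the SAP's arguments (run in R 4.3.3, not the R 3.5.0 of the SAP). There were 40 data sets per scenario, each re-tuned with 20 seeds on identical data. Each cell gives the share of data sets in which the seed alone changed the selected set / switched it between empty and non-empty.

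| n | p | R² | lambda.min | lambda.1se | Fewest–most features over seeds, lambda.min (medians over data sets) |
|---|---|---|---|---|---|
| 36 | 131 | 0 | 68% / 53% | 20% / 20% | 0–6 |
| 36 | 131 | 0.3 | 93% / 60% | 47% / 45% | 0–12 |
| 36 | 131 | 0.6 | 95% / 12% | 85% / 38% | 7–24 |
| 36 | 81 | 0.3 | 95% / 42% | 55% / 42% | 1–15 |
| 36 | 231 | 0.3 | 80% / 45% | 30% / 28% | 0–10 |
| 41 | 131 | 0.3 | 93% / 45% | 53% / 50% | 0–13 |

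With 40 data sets, a share near 50% has a standard error of about √(0.5 × 0.5 / 40) = 0.08, so the percentages are approximate.

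**Does the list change in content or in length?** On fixed data the split moves only λ; the coefficients come from one Lasso path fitted to everyone. A separate simulation (n=36, p=131, five true predictors, R² 0.4, 25 data sets × 25 splits, lambda.min) compared the non-empty sets that differed. On average 98% of the smaller set lay inside the larger, and 77% of such pairs were fully nested. Occasional pairs did not overlap. The number selected had a median range of 1 to 26.

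**The λ rule.** At n=36, p=131 and R² 0.3, the median set size was 4.8 at lambda.min and 0 at lambda.1se. This unstated choice is a second source of difference between analysts, apart from the split.

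**Remedies** (n=36, p=131, R² 0.3, 12 data sets × 5 seeds, lambda.min):

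| Tuning | Set changed with seed | Empty/non-empty switch |
|---|---|---|
| One 10-fold split | 92% | 42% |
| Error curve averaged over 10 splits | 42% | 8% |
| Leave-one-out (nfolds=n) | 0% | 0% |

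In a further simulation at R² 0.4 with five true predictors, two independent averages over 20 splits differed by a median of 0.5 features (90th percentile 2).

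**The case against.** A reader might infer that different seeds would name different species and amino acids. The simulations do not support that as the usual outcome: different splits mostly lengthen or shorten one list.

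A reader might also infer that the analysts make a single unseeded call. The documents only fail to mention repetition or a seed. This stands as a limit on the wording. A fixed seed would make the run reproducible but would leave the result tied to one arbitrary split.

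The sizes rest on an assumed species count and signal. That also stands, and it is why ranges are given. With strong signal at lambda.min, the empty/non-empty switch falls to 12%.

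The strongest objection concerns the stakes. The Lasso is neither a primary nor a secondary outcome. The BMI tests, the amino acid and taxa comparisons and the sample size are untouched. This is accepted and sets the grade.

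It might be said that the leave-one-out step already deals with the problem. It does not. It is run on features chosen beforehand from all participants, so it neither retunes λ nor repeats the selection. If selection were nested inside it, each outer fold would still tune on a random split.

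**Conclusion.** The point holds, as a minor one. As written, the tuning leaves the number of selected omics features, and sometimes whether there are any, dependent on a random fold split that the plan neither fixes nor averages over.

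The direction was the same in every scenario. The size was not: across both λ rules, the set changed in 20–95% of data sets and switched between empty and non-empty in 12–60%. These figures depend on an assumed number of species, an assumed signal and Gaussian features. The documents do not allow the effect on the trial's own data to be estimated. The consequence is confined to the exploratory prediction analysis.

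**What to change.** In SAP section 6 and Protocol 6.1, replace the tuning sentence with one of two rules:

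- Run the 10-fold cross-validation over many random fold assignments (for example 100), average the error curves, and take λ at the minimum of the averaged curve. The number is a judgement: averages over 10 and 20 splits were checked, and 10 left the set changing in 42% of data sets.
- Tune by leave-one-out (nfolds=n). This is one changed argument and has no random split. It removes dependence on the seed, not sampling uncertainty.

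In either case, state the λ rule and the seed, and apply the same rule wherever λ is tuned. State that if no feature is selected, the result is reported as no omics predictor and no rho is calculated. An intercept-only leave-one-out prediction for person i is (Σy − y_i)/(n − 1). It falls as y_i rises, so rho would be −1 by construction.

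If the share of splits that select each feature is reported, label it as sensitivity to the fold split. It is not feature stability, which would need resampling of participants.

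The cost is a short loop and a few sentences, with no new data. The feature list may become shorter or empty. The change does not remove the separate optimism in rho that comes from running leave-one-out on features already selected from all participants.
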